1.1 ExAblate delivery of MR guided Focused Ultrasound (MRgFUS) [1]

MRgFUS is an attractive modality for non-invasive thermal ablation of soft tissue tumors [2-6]. Treatment begins by acquiring a series of MR images of the target organ. The physician then reviews the images on the ExAblate system workstation, identifies a target volume on the MR images, delineates the treatment contours on the images, and reviews the treatment plan. Therapy planning software calculates the parameters required to effectively treat the defined region. During the treatment, an ultrasound transducer generates a point of focused ultrasound energy, called a *sonication* (See **Appendix-A** for Glossary of Terms). The sonication raises the tissue temperature within a well-defined region, causing a thermal coagulation effect. MR images acquired during sonication provide a quantitative, real-time temperature map of the entire field-of-view around the target area to confirm the location of the sonication and the size of the coagulated region. The sonication process is repeated at multiple adjacent points to cover the entire prescribed treatment volume.

1.2 Metastatic Bone Tumors

Bone is the third most common organ involved by metastatic disease behind lung and liver [7]. Breast and prostate cancer metastasize to bone most frequently, which reflects the high incidence of both these tumors, as well as their prolonged clinical courses.

The increasing longevity of the population coupled with better therapeutic management of cancer patients contributes to the high incidence and prevalence of metastatic bone lesions. Pain from bone metastases is the most common cause of cancer pain and as more patients are living with bone metastases, improving their quality of life becomes a major challenge. In patients who die from breast, prostate, and lung cancer, autopsy studies have shown that up to 85% have evidence of bone metastases at the time of death [7-9].

Current treatments for patients with bone metastases or multiple myeloma bone lesions are primarily palliative and include localized therapies [10], systemic therapies (chemotherapy, hormonal therapy, radiopharmaceutical, and bisphosphonates), and analgesics (opioids and non-steroidal anti-inflammatory drugs). Recently, radiofrequency ablation has been tested as a treatment option for bone metastases [11]. The main goals of these treatments are improvement of quality of life and functional level. These goals can be further described:

Pain relief

Preservation and restoration of function

Local tumor control

Skeletal stabilization

Treatment with external beam radiation therapy (EBRT) is the standard of care for patients with localized bone pain, and results in the palliation of pain in the majority of these patients. More than 66% of patients with a limited number of well-localized bony metastases can be treated effectively by external-beam irradiation. However, approximately 30% of patients treated with radiation therapy do not experience pain relief [8, 12-16]. Furthermore, there is an increased risk of pathologic fracture in the peri-irradiation period due to an induced hyperemic response at the periphery of the tumor. This weakens the adjacent bone and increases the risk of spontaneous fracture. Adding to this, patients who have recurrent pain at a site previously irradiated may not be eligible for further radiation therapy secondary to limitations in normal tissue tolerance. The speed of response to radiation therapy varies; most symptomatic bony metastases begin to respond over the course of 10 to 14 days, 70% of patients experience some pain relief within 2 weeks of starting therapy and, within 3 months 90% of the responding patients achieve pain relief.

Patients, who had EBRT and failed to improve, may need to seek other therapies such as radio frequency ablation, surgical resection, etc., which are less efficient and have higher treatment related morbidity. Because the ExAblate system is designed to non-invasively ablate tissue, ExAblate may meet the need of these EBRT failed patients. The ExAblate system has the potential to achieve the first three of the four above mentioned goals, as well as changing the treatment limits and resulting morbidity in accordance with the above-mentioned goals [17]. The palliative effect of ExAblate is achieved by heating the bone periosteum, thus ablating the sensory origin of the pain and has the potential to achieve some tumor control.

Based on the FDA approved phase-1 initial study (IDE # G050177) results and the results of the study that was performed outside the United States that the sponsor has done, palliation effects are significant in terms of mean improvement, the percent of treated patients who reported symptomatic improvement and in the treatment durability.

1.3 The ExAblate System

The ExAblate system is a non-invasive thermal ablation device that has been used for the ablation of tissue. This system combines a focused ultrasound surgery delivery system and a conventional diagnostic 1.5 T or 3T MRI scanner to implement MR guided focused ultrasound surgery (MRgFUS). The ExAblate system provides real-time therapy planning algorithm, thermal dosimetry, and closed-loop therapy control. The latter is achieved by utilizing the unique interactive MRI scan control features of the GE MRI system. The

ExAblate device is an integrated component of the MR table. The subject is placed on the MRI table and moved into the MRI scanner.

The treatment process begins with the physician acquiring a set of MR images, identifying target volume(s), and drawing the treatment contours. The therapy planning software computes the type and number of sonications required to treat the defined region while minimizing total treatment time. MR images taken during the sonication provide a diagnostic quality image of the target tissue and a quantitative, real-time temperature map overlay to confirm the therapeutic effect of the treatment in real time. The transducer is then automatically moved to the succeeding treatment point and the process is repeated until the entire volume has been treated. Typically, ~30 individual sonications can be delivered over approximately 2 hours period to complete a metastatic bone tumor treatment.

1.4 Clinical Experience with ExAblate

Uterine Fibroids (UF) – FDA Approved Indication

The ExAblate 2000 system received FDA approval for the treatment of UF in November 2004 (PMA #P040003). The ExAblate 2000 had previously received CE Mark (European Authority approval and others) and AMAR authorization (Israel Ministry of Health) for the indication of treating UF. To date, approximately 8,000 treatments for uterine fibroids has been performed worldwide. Since its approval, a number of other studies have been completed or are in process to assess changes in software and hardware or to provide additional information to support labeling changes.

EXABLATE NEW SOFTWARE VALIDATION (IDE #G050221)

This was an FDA-approved study to validate the new ExAblate application software as well as the use of the ExAblate system with 3T MR scanners for the treatment of UFs. This was only a safety study. A total of 40 subjects were treated under this protocol IDE. The PMA-S was approved on February 27, 2007 under P040003/S002

ENHANCED SONICATION PROTOCOL (IDE #G060017)

This was an FDA-approved study to validate the new Enhanced Sonication feature of the ExAblate system, a detachable cradle, and several other modifications to the ExAblate 2000 system. This was a safety study only. A total of 50 subjects were treated under this protocol IDE. Following completion of this study, a full PMA supplement was submitted to FDA for review and approval [PMA# P040003]. Approval was granted on 12/22/2009 under PMA Supp P040003/S006. The system is marketed under the trade name ExAblate 2000/2100 and is indicated for use in treating symptomatic uterine fibroids.

ENHANCED SONICATION POST MARKETING STUDY-P040003/S007

InSightec is currently recruiting subjects for a post-market study using the FDA approved enhanced sonication feature to demonstrate the safety of the enhanced sonication feature

within current treatment guidelines of 100% individual fibroid ablation within established serosal and sacral treatment margins; this study will enroll 115 subjects and is nearing completion (P040003/S007).

VALIDATION OF EXABLATE UF V2 – IDE G100127.

InSightec is currently recruiting centers and initiating IRB review for study conduct in order to gain approval for the ExAblate Model 2100 Type 1.1 (also refer to as ExAblate UF V2). This ExAblate system will be operated with a NEW Clinical Application SW utilizing the added 5th degree of freedom of the transducer (A/P movement) in its overall planning and treatment of the uterine fibroids. This study will enroll 106 subjects under IDE # G 100127.

Malignant and Benign Breast Studies – Investigational

MRGFUS EXABLATE ABLATION OF BREAST CARCINOMA: CLINICAL STUDY WITH EXCISION

InSightec conducted FDA approved clinical trials under IDE # G990184 and G990201 to evaluate the safety and efficacy of the ExAblate system in the ablation of breast carcinomas [1-3]. These are studies are closed. Of all the patients treated, only three patients experienced non-significant adverse effects: one patient with mild event of redness at the ablation site, a second patient with mild event of firmness, and a third patient with a 3rd degree skin burn that was due to operator's targeting error and not due to the device.

MRGFUS EXABLATE ABLATION OF BREAST FIBROADENOMA

InSightec conducted a feasibility FDA approved clinical trials under IDE # G930140 to evaluate the safety and efficacy of the ExAblate system in the ablation of breast fibroadenoma [4]. Following this feasibility study, InSightec initiated an FDA approved pivotal protocol to study ExAblate ablation of Breast Fibroadenoma (IDE # G010225). A total of 110 patients were approved for this trial, and only 27 patients were treated before the study was closed for enrollment due to lack of subjects enrollment. No unanticipated adverse effects have been reported or detected by MRI. Clinically, acute pain and discomfort were tolerable, and no long-term complications occurred.

ExAblate Transcranial Brain Studies – Investigational

EXABLATE MRGFUS TRANSCRANIAL TREATMENT OF BRAIN TUMORS: IDE # G020182 – EXABLATE TCMRGFUS LOW FREQUENCY SYSTEM

In 2002, the FDA approved an IDE for a feasibility safety clinical study for the ExAblate Transcranial MRgFUS system in the treatment of brain tumors. This study is currently enrolling. A total of 10 patients will be treated under this IDE.

EXABLATE TRANSCRANIAL MRGFUS THALAMOTOMY FOR MEDICATION REFRACTORY ESSENTIAL TREMOR PATIENTS

InSightec received FDA approval for a feasibility of ExAblate Transcranial MRgFUS for unilateral thalamotomy in the treatment of Essential Tremor under IDE # - G100169. Total of 15 patients were treated. This study is currently on-going and 10 out of the 15 patients have been treated to date. Based on the investigator and the patient's feedback, patients have shown a great level of acceptance of the procedure. Furthermore, patients have shown a significant improvement in their Essential Tremor disease following their treatment with the ExAblate Transcranial MRgFUS device. Patients who completed the study requirements have shown stability of the tremor suppression all the way to the end of the study.

Bone Feasibility Study IDE# G050177

The objective of this trial was to evaluate the safety and effectiveness of using ExAblate as a treatment for pain palliation in patients with metastatic bone tumors. This study was designed as a prospective, one arm, non-randomized study. Ten subjects were enrolled at two sites. Nine subjects completed the study; one subject could not complete treatment due to limited device accessibility to the lesion. This study served as the basis for the Pivotal IDE study (IDE # G070022).

**EXABLATE CONFORMAL BONE SYSTEM (CBS) STUDY SUMMARY – FDA STUDY:
IDE G 080206**

InSightec is currently conducting this study at three sites. The study is enrolling and to date, seven subjects have been enrolled and treated with this conformal system. The study was cleared for 50 subjects. The study is still on-going. Although no data is available at this time, all the informal information from the participating investigators is that there is a very high level of patient acceptance of the ExAblate procedure. To date, the safety profile continues to be favorable to the ExAblate procedure, and there were no new events that may be attributed to the device.

BONE PIVOTAL STUDY IDE # G070022 – REVIEWED UNDER PMA P110039

This study was designed as a prospective, randomized (3 ExAblate :1 Sham), single-blind multicenter sham-controlled clinical trial comparing ExAblate treatment against a Sham treatment with follow-up post-treatment to three months. A total of 148 patients were enrolled and treated under this IDE. This IDE study is under review under PMA # P110039.

2 OBJECTIVES

2.1 Background

As part of the PMA # P110039 review process and approval, InSightec was requested to conduct a post-approval study. Patients will be treated following the approved commercial treatment guidelines.

For this study, participating sites will use the ExAblate device for the administration of the ExAblate treatment. This study will be performed on either 1.5T or 3T MR scanners.

For this study, a total of 70 patients meeting the approved commercial guidelines will be enrolled and treated with the ExAblate system at from 7 to 10 sites. The proportion of responders is expected to be at least 30% greater than the proportion of subjects experiencing pain progression (i.e., 60% vs. 30%). Additionally, at the 3 month visit, an analysis of both the safety and efficacy profiles will be compared to the original PMA pivotal study group. This comparison will be descriptive with no statistical endpoints.

2.2 Safety

Safety of ExAblate will be determined by an evaluation of the incidence and severity of device related complications from the first treatment day visit through the 3-Months post-treatment time point.

2.3 Effectiveness

This study will follow the gold standard end points as stated by the “International consensus on palliative radiotherapy endpoints for future clinical trials in bone metastases” [11, 24, 25]. For this purpose, this study will:

- Capture patient based pain assessment using a 0-10 pain Numerical Rating Scale (NRS) with anchored points in conjunction with a body diagram.
 - Define “pain relief” complete response as a pain score of zero (0) at the treated site without increase in analgesic consumption.

- Define “pain relief” partial response as a reduction of 2 points on a 0–10 scale at the treated site without increase in the analgesic consumption¹.
- Capture the dosage and frequency of analgesics/opiate consumption from baseline through the 3-Months post-treatment follow-up visit for each patient.
- Capture the Quality of Life of each treated patient using the standard Brief Pain Inventory Questions 9A-G (BPI-QoL).
- Following ExAblate treatment have 1-week, and 1, 2, and 3 months follow-up time points.
- Response will be analyzed at 3 months.

Efficacy Assessments

Efficacy assessments used in this study are based on The International Bone Metastases Consensus Working Party on endpoint measurements [11, 24, 25] which recommends a 0-10 point scale such as the NRS or BPI and to include a body diagram.

NUMERICAL RATING SCALE (NRS)

The Numerical Rating Scale is a validated standard instrument widely used for the assessment of cancer pain and have been used to investigate the effectiveness of radiation therapy to relieve pain resulting from bone metastases [26, 27].

We propose to use the NRS to capture pain change at the treatment site during the course of the study and to use a human figure for patients to mark the location of pain [24, 25]. The worst pain NRS will be used to assess pain in the present study and will include a body diagram for marking areas of pain. Additionally, the average pain NRS scores will be collected. Quality of life (BPI-QoL) and medications use will also be captured. Narcotic medications will be converted to morphine equivalents (**Appendix D**)

BPI_QUALITY OF LIFE (BPI_QoL)

To assess the impact of bone pain following targeted/localized treatment on health-related quality of life, the pain interference scale from the BPI-QoL will be included [**Appendix E**]. Pain interference refers to the extent to which pain interferes with day-to-day functioning and is more likely to be sensitive to anticipated changes in the health-related quality of life among the study population. The most common measure of cancer pain interference is the BPI -QoL[30]. This is a validated scale consisting of 7 items that ask respondents to indicate the extent to which pain interferes with general activity,

¹ Meds increase is defined as a change of 25% ¹or more in MEU; per Chow, E., et al., International consensus on palliative radiotherapy endpoints for future clinical trials in bone metastases. Radiother Oncol, 2002. 64(3): p. 275-80

mood, walking ability, normal work, relations with other people, sleep, and enjoyment of life”.

2.4 Study End Points

Safety

A full safety profile will be developed for the ExAblate treatment of bone metastases. All adverse events will be captured and summarized as defined in **Section-6.2**. Adverse events (type, frequency, severity) are expected to be similar to those captured for the original PMA study (PMA # P110039).

For his study, the Safety comparison with the data of the Pivotal (IDE Study G070022) study will be descriptive with no statistical endpoints.

Efficacy

A full efficacy profile will be developed for the ExAblate treatment of bone metastases. For this study efficacy will be determined by comparing outcomes at the 3 month visit to baseline within subjects. Additionally the safety and efficacy of treatment Responders and Non-Responders will be tabulated, and compared with that of the original PMA (P110039).

The primary endpoint is the proportion of responders at the 3 month study visit.

Definition of terms:

- Patient Responders: these are all ExAblate treated patients who experience at least a 2 point improvement from baseline on NRS at the treated site without increase in medications
- Patient Non-Responders: these are all ExAblate treated patients who experience less than 2 points improvement from baseline to 3 months on the NRS at the treated site without increase of medication or increased medications.
- Patient Pain Progression: these are all ExAblate treated patients who either experience 2 points worsening from baseline to 3 months on the NRS at the treated site or who increase morphine equivalence 25% or more. Pain progression is a subset of non-responders.

Secondary Endpoints

This study has two secondary end points. The goal of these secondary end points is to assess the impact of the ExAblate treatment of painful bone Mets on the overall quality of life and clinical benefits to ExAblate MRgFUS treated patients:

Quality of life outcomes of all treated patients will be captured during the course of the study. A comparison between baseline and 3 months post-ExAblate treatment of the BPI-QoL will be performed.

Pain Medications of all patients will be captured and summarized. Changes in narcotic medications will be expressed in morphine equivalents.

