5 STATISTICAL ANALYSIS PLAN

This study is a designed as a single arm within subjects comparison of outcomes at the 3 month visit to baseline. For this study, a total of 70 patients meeting approved

commercial guidelines for bone metastases will be enrolled and treated with the ExAblate system at from 7 to 10 investigational sites.

Safety

A full safety profile will be developed for the ExAblate treatment of bone metastases. All adverse events will be captured and summarized as defined in **Section-6.2**. Adverse events (type, frequency, severity) are expected to be similar to those captured for the original PMA study (PMA # P110039). For this study, the Safety comparison will be descriptive with no statistical endpoints.

Efficacy

A full efficacy profile will be developed for the ExAblate treatment of bone metastases. For this study efficacy will be determined by comparing outcomes at the 3 month visit to baseline within subjects. Also, the outcomes will be compared with the original efficacy data of the PMA (P110039), where the proportion of treatment Responders and Non-Responders will be tabulated and compared.

The statistical hypothesis is that the proportion of responders will be significantly greater than the proportion of subjects experiencing pain progression (worsened pain or increased pain medications usage) by at least 30% or an odds ratio of at least 2.

Secondary Endpoints

Medications use and quality of life will be analyzed as secondary endpoints.

PATIENT GENERAL HEALTH STATUS

Patient overall quality of life status will be assessed by the BPI-QoL Pain Interference scale which will be administered pre-treatment and post-treatment. The trajectory of change may be analyzed descriptively by regression slopes.

BASELINE DATA ANALYSES

Baseline clinical, demographic and patient reported outcome characteristics will be tabulated and compared descriptively to the original PMA.

HEALTH COST AND SERVICES UTILIZATION

Summary tabulations and figures may be developed for reimbursement purposes only.

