5.2 Statistical Considerations and Sample Size

The primary goal of the study is to evaluate the safety and efficacy of the ExAblate palliative treatment of painful bone metastases. This study will be conducted with both the 1.5T and 3T MR scanners. Seventy (70) patients will be enrolled and treated; enrollment will continue at from 7-10 research sites.

A sample size analysis was performed using the McNemar Test Power Analysis from the PASS² program using parameters from the pivotal PMA study (PMA # P110039). The response rate in the USA was 18/30 = 60%. The proportion of non-responders experiencing pain progression was 30%. Thus, the proportion discordant was 90%. Given $\alpha = 0.025$ for a one-sided hypothesis, $1 - \beta = 0.7$ requires a sample size of 65 subjects to detect an odds ratio of 2.0. The odds ratio is equivalent to a difference between two paired proportions of 0.30 which occurs when the difference in the proportion of responders (60%) is 30% greater than the proportion of subjects experiencing pain progression (30%). In order to account for potential dropouts 70 subjects will be initially enrolled in the study.

The hypothesis can be specified as follows:

$H_0: P10 = P01$. $H_1: P10 > P01$, where $P10$ is the proportion of subjects that respond (improve by 2 points without increasing medications) and $P01$ is the proportion of subjects that worsen.

Subject Confidentiality

Subject confidentiality will be maintained throughout this study, including all publications. Data collected and entered into the CRFs are the property of the study sponsor. Representatives from the study sponsor or authorized sponsor representatives, the Institutional Review Board (IRB), Ethics Committee or the FDA may receive copies of the study records and may review medical records related to the study.

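### The named primary endpoint is the responder proportion, but the only formal test compares responders with progressors, so a positive test shows direction and not the level of response

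*Combined protocol and SAP*

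**What the plan says.** Section 2.4 (Study End Points, Efficacy) names one primary endpoint: "The primary endpoint is the proportion of responders at the 3 month study visit". Its definitions cover all treated patients. Non-responders include those with no increase in medication whose improvement is too small: "these are all ExAblate treated patients who experience less than 2 points improvement from baseline to 3 months on the NRS at the treated site". It adds: "Pain progression is a subset of non-responders". A patient who neither improves by 2 points nor worsens is therefore a failure on this endpoint.

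Section 5 (Efficacy) states the hypothesis differently: "The statistical hypothesis is that the proportion of responders will be significantly greater than the proportion of subjects experiencing pain progression", with the effect size given as "by at least 30% or an odds ratio of at least 2". Section 5.2 sizes the study with a McNemar power calculation. Its formal hypotheses are H0: P10 = P01 against H1: P10 > P01, where P10 is the proportion responding and P01 the proportion worsening; no margin appears.

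Section 5 also tabulates responders and non-responders beside the original PMA data. Section 2.1 says that this comparison is descriptive.

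**The concern.** The endpoint is a single proportion with every treated patient in the denominator. The test is a contrast between two of three outcome groups. The two can move apart: at a fixed response rate, the test becomes easier to win as non-responders shift from progression to stability.

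No confidence interval, null value or test is attached to the responder proportion itself. The study's one inferential result would therefore not describe the endpoint that Section 2.4 calls primary, and a significant result could be reported as success on response when it shows only which of two groups was larger.

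**Working it through.** **Inputs (Section 5.2).** P10 = 0.60 (18/30 in the US pivotal data), P01 = 0.30, proportion discordant 0.90 (hence 10% stable), one-sided alpha 0.025, power 0.70, n = 65, with 70 enrolled. Section 5.2 names McNemar for sizing; I take it as the intended test.

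**Step 1: the plan's own figure.** With d = 0.60 − 0.30 = 0.30 and pd = 0.90:

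n = [z(0.975)·√pd + z(0.70)·√(pd − d²)]² / d² = [1.960·√0.90 + 0.524·√0.81]² / 0.09 = 60.4.

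Adding a continuity correction of 1/d = 3.3 gives 63.7, so 64. Exact power at n = 65 is 0.69. The stated 65 subjects for 70% power is reproduced.

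**Step 2: which results reject.** Given r responders and s progressors, the exact test rejects when P(X ≥ r) ≤ 0.025 for X ~ Binomial(r + s, 0.5). Stable patients appear nowhere in this rule. At n = 65, with Clopper-Pearson intervals for r/65:

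| Responders v progressors | Stable | One-sided p | Response (95% CI) | Ratio r/s | Difference (r − s)/65 |
|---|---|---|---|---|---|
| 15 v 5 | 45 (69%) | 0.021 | 23% (14–35%) | 3.0 | 15.4 points |
| 20 v 8 | 37 (57%) | 0.018 | 31% (20–43%) | 2.5 | 18.5 points |
| 36 v 20 | 9 (14%) | 0.022 | 55% (43–68%) | 1.8 | 24.6 points |

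Each row has the smallest r that rejects for its s. The last row is at about the planned progression (0.30 × 65 = 19.5).

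**Step 3: probability of a positive test.** Power is the sum over D ~ Binomial(65, P10 + P01) of the rejection probability given D, where responders given D are Binomial(D, P10/(P10 + P01)).

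| True response / progression | H0: P10 = P01, no margin | Also requiring an observed difference of at least 30 points |
|---|---|---|
| 60% / 30% (planned) | 0.69 | 0.51 |
| 30% / 10% | 0.68 | 0.09 |

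Under the margin-free H0, half the planned response rate gives nearly the same chance of a positive test.

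**Step 4: Section 5's effect-size clause.** Its two conditions are joined by *or*. Read as a point estimate, an odds ratio of at least 2 is met by both 15 v 5 and 20 v 8. An observed 30-point difference needs r − s ≥ 19.5, so 20 patients; neither example meets that, but 25 v 5 does (20/65 = 30.8 points, response 25/65 = 38%).

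**The case against.** The responder-versus-progressor contrast is stated openly and consistently in Sections 2.1, 5 and 5.2, using terms defined in 2.4. A single-arm study can test a lone proportion only against a performance goal, and the documents give none. This stands as a reason to keep the powered test. It does not supply an estimate with uncertainty for the endpoint named primary.

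The low-response examples need 57% to 69% stable patients, whereas the plan implies 10%. This also stands: near the planned progression the lowest winning rate is 55%. But the planning rates rest on 30 patients (exact 95% CI for 18/30: 41–77%), so another split is plausible.

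Section 5's clause might block weak results. As an added requirement of an observed 30-point difference, it largely does (0.68 falls to 0.09). If it meant significantly above an odds ratio of 2, neither 15 v 5 nor 20 v 8 would pass (exact p = 0.30 and 0.38). That last reading does not fit Section 5.2, which claims 70% power at an odds ratio of exactly 2.0; with 2 as the null value, rejection there could not exceed 2.5%. The clause is unclear, and 5.2 carries no margin.

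A reader might infer that the trial must show 60% and can pass while missing it. The documents do not support this: 60% is a sizing assumption. A reader might also infer that stable patients are ignored altogether. They remain in the denominators of P10 and P01, and so reduce the difference; they drop out only of the McNemar statistic.

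**Conclusion.** The mismatch is explicit in the text and should be corrected. A positive P10 versus P01 test supports the statement that more patients responded than progressed; it establishes nothing about the level of the primary endpoint.

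How far the two can separate is conditional. Under the margin-free H0, with n = 65 and the exact one-sided 0.025 test, a 23% or 31% observed response can win if few patients progress. At about 20 progressors the minimum is 55%. If an observed 30-point difference is also required, the gap narrows but remains, since 25 v 5 (38% response) would pass. The sample-size arithmetic is sound for the test chosen and is not part of this point.

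**What to change.** In Section 5:

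- Report the responder proportion among all treated patients with an exact 95% confidence interval as the estimate of the primary endpoint. For illustration, 39/65 would give 60% (47–72%). Do not treat 60% as a pass mark.
- Keep the P10 versus P01 test, and state that it is a test of direction whose conclusion is worded *more patients responded than progressed*.
- Make the hypothesis agree with the margin-free H0 in Section 5.2, so that the 30% and odds-ratio figures are not left as an ambiguous success condition.
- Always present the responder, stable and progression proportions together.

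The cost is SAP wording and one interval, with no new data or patients. The downside is that a significant direction test may sit beside a modest or imprecise response rate.
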